PASS information

Title	Monitoring safety of Spikevax in pregnancy: an observational study using routinely collected health data in five European countries
Protocol version identifier	Version 1.2
Current date of protocol	27 September 2021
EU PAS register number	Protocol will be registered before start of the data collection
Active substance	COVID-19 mRNA-1273 vaccine (nucleoside modified)
Medicinal product	COVID-19 Vaccine Moderna/Spikevax
Product reference	EMA/H/C/005791
Procedure number	MEA 034
Marketing authorisation holder(s)	Moderna Biotech Spain, S.L. [name]
Joint PASS	No
Research question and objectives	
The overarching research question is: is there a greater risk or prevalence of pregnancy complications, adverse pregnancy outcomes, or adverse neonatal outcomes following pregnancies exposed to Spikevax compared with pregnancies unexposed to Spikevax?
 
Primary objectives:
 
 • To determine whether exposure to the Spikevax during pregnancy is associated with an increased risk of: 
 a. Pregnancy complications b. Adverse pregnancy outcomes c. Major congenital malformations in the offspring (overall and organ-specific if feasible) d. Adverse neonatal outcomes

	Secondary objectives 
• To describe utilization of Spikevax in pregnancy
Country(-ies) of study	Denmark, Italy, Norway, Spain, United Kingdom
Authors	

Marketing authorisation holder(s)

Marketing authorisation holder(s)	ModernaTX, Inc.
MAH contact person	<hr/> <hr/>

1. Table of contents

PASS information	1
1. Table of contents	4
2. List of abbreviations	6
3. Responsible parties	8
4. Abstract	11
5. Amendments and updates	13
6. Milestones	15
7. Rationale and background	16
8. Research question and objectives	17
9. Research methods	17
9.1. Study design	17
9.1.1 Prevalence study	17
9.1.2 Cohort study	18
9.2. Setting	18
9.3. Variables	19
9.3.1 Exposure	19
9.3.2 Outcome	20
9.3.1 Covariates	21
9.3.2 Subgroups	21
9.4. Data sources	22
9.5. Study size	23
9.6. Data management	24
9.7. Data analysis	25
9.7.1 Descriptive analyses	25
9.7.2 Measures of occurrence and measures of association	25
9.7.3 Subgroup analyses	29
9.7.4 Sensitivity analyses	29
9.7.5 Data integration	29

Confidential

Post-marketing safety study for COVID-19 mRNA-1273 vaccine

Protocol mRNA-1273-P905, Date: 27 September 2021, Version 1.2

9.8 Quality control	30


[name]
 <hr/> 
Aarhus University, Principal Investigator
	 <hr/> 
Signature
	
Professor, Chair
 <hr/> 
Title
	
04-Nov-2021
 <hr/> 
Date

4. Abstract

Title

Monitoring safety of Spikevax in pregnancy: an observational study using routinely collected health data in five European countries

mRNA-1273-P904, Protocol Draft Version 1.1, 19 August 2021

[name], Aarhus University, Denmark

Rationale and background

The novel coronavirus SARS-CoV-2 (severe acute respiratory syndrome coronavirus 2) causes coronavirus disease 2019 (COVID-19) and has led to a global pandemic. A mass vaccination campaign is currently underway in Europe. The mRNA-1273 vaccine, currently known as Spikevax,¹ combines Moderna's mRNA (messenger ribonucleic acid) delivery platform with the stabilized SARS-CoV-2 spike immunogen, developed by NIAID.

Research question and objectives

The overarching research question is: is there a greater risk or prevalence of pregnancy complications, adverse pregnancy outcomes, or adverse neonatal outcomes following pregnancies exposed to Spikevax compared with pregnancies unexposed to Spikevax?

Primary objectives:

- To determine whether exposure to the Spikevax during pregnancy is associated with an increased risk of:
 - a. Pregnancy complications
 - b. Adverse pregnancy outcomes
 - c. Major congenital malformations in the offspring (overall and organ-specific if feasible)
 - d. Adverse neonatal outcomes

Secondary objectives

- To describe utilization of Spikevax in pregnancy

Depending on the outcome, either a prevalence design (all endpoints except pregnancy-related death and neonatal death) or cohort design (pregnancy-related death and neonatal death) will be used to address each objective.

Study design

The maternal and pregnancy outcomes will be addressed using the prevalence study design; neonatal outcomes and pregnancy related death in the cohort design. In the routinely collected data, pregnancies are typically identifiable on the date of pregnancy end, either in a birth or in an abortive outcome. All identifiable pregnancies will be included, and their start and end dates will be determined based on the LMP or gestational age at end, depending on data availability. Outcomes examined in this design include gestational diabetes, hypertensive disorders of pregnancy, pregnancy-related death, fetal growth restriction/small for gestational age, spontaneous abortion, stillbirth, preterm birth, major congenital malformations, microcephaly, neonatal death, and termination of pregnancy for foetal anomaly (TOPFA).

Population

This study will be multi-database, utilizing routinely collected health data of various types in five European countries: Denmark, Italy, Norway, Spain, and the United Kingdom. Pregnancies ending between 6 January 2021 (date of the earliest approval of the COVID-19 Moderna Vaccine in Europe) and 31 December 2022 will be identified and classified according to the exposure to the COVID-19 Moderna Vaccine, overall and according to the trimester of exposure. The study period may be extended if the size of the study population is insufficient to study specific outcomes of interest.

The study population will encompass all pregnancies, identifiable in the databases, ending in a live or still birth, a spontaneous abortion, or an induced abortion, as identifiable in the participating databases. In Denmark and Norway, all pregnancies ending in a live or still birth, as well as pregnancies leading to a hospital encounter due to termination will be identifiable.

Variables

Members of the analysis populations (pregnancies, births, depending on the outcome) will be described with respect to available demographic characteristics, medical history, medication use, receipt of other vaccines, and characteristics of the exposed pregnancy. Pregnancies and births will be classified according to the exposure status Spikevax, overall and by trimester.

The outcomes of interest will include pregnancy complications, adverse pregnancy outcomes, and adverse neonatal outcomes.

Covariates will include maternal pre-pregnancy demographic and clinical characteristics, such as age, smoking, body mass index, chronic morbidities and medication use.

Data sources

This study is planned as analysis of routinely collected health data in secondary automated electronic data sources in Denmark, Italy, Norway, Spain, and the UK, selected based on availability of the required routinely collected data, including information on vaccine brand and frequency of data updates.

Study size

It is estimated that the number of live births available for analysis will range between 20,000 to 100,000 depending on a data source.

Data analysis

Counts and percentages will be presented for categorical variables (woman's age at conception in categories). Means, standard deviations, medians and interquartile ranges will be presented for continuous variables (woman's age at conception). The proportion of missing data will be described when appropriate. For pregnancy complications and adverse pregnancy outcomes, pregnancy will be the unit of observation; for neonatal outcomes, a newborn will be the unit of observation. For the outcomes of congenital malformations and stillbirth, the number at risk will be the total number of live or stillborn children.

Prevalence of each outcome will be computed as number of observations with a given outcome divided by the total number of observations at risk. Prevalence of each outcome will be compared for exposed vs. unexposed pregnancies according to predefined exposure categories and using, whenever necessary, plausible exposure risk windows. For example, for assessing the outcome of congenital malformations, maternal gestational diabetes and hypertensive disorders, births or pregnancies will be classified based on their exposure in the first (or second, if relevant) trimester. For all other neonatal outcomes, exposure any time in pregnancy and per trimester may be considered.

For neonatal deaths, 28-day mortality risks will be computed and compared among live-born neonates. For pregnancy-related death, maternal mortality will be evaluated at any time while pregnant or up to 1 year after pregnancy end.

All relevant analyses will be stratified by country, maternal age, sex, calendar time, trimester and seasonality if applicable.

Milestones

Data collection will continue through 31 March 2023 with a final study report planned by December 2023.

5. Amendments and updates

Write "None" or indicate any substantial amendment and update to the study protocol after the start of data collection in a table as indicated below.

Confidential

Post-marketing safety study for COVID-19 mRNA-1273 vaccine

Protocol mRNA-1273-P905, Date: 27 September 2021, Version 1.2

Number	Date	Section of study protocol	Amendment or update	Reason
1	Date	Text	Text	Text
2	Date	Text	Text	Text
...	Date	Text	Text	Text

6. Milestones

Milestone	Planned date*
Start of data collection	31 December 2021
End of data collection/data cut for Final report of study results	31 March 2023
Study progress report 1	31 March 2022
Study progress report 2	31 December 2022
Study progress report 3	30 June 2023
Registration in the EU PAS register	Upon approval
Final report of study results	31 December 2023

* Subject to data queues by data custodians; progress report will contain information on study progress and data updates whenever available.

7. Rationale and background

The novel coronavirus SARS-CoV-2 (severe acute respiratory syndrome coronavirus 2) causes coronavirus disease 2019 (COVID-19) and has led to a global pandemic. A mass vaccination campaign is currently underway in Europe.

The mRNA-1273 vaccine candidate was co-developed by the Cambridge, Massachusetts-based biotechnology company Moderna, Inc., and the United States (US) National Institute of Allergy and Infectious Diseases (NIAID), part of the National Institutes of Health. The vaccine, currently known as Spikevax,¹ combines Moderna's mRNA (messenger ribonucleic acid) delivery platform with the stabilized SARS-CoV-2 spike immunogen, developed by NIAID.

The completed COVE Phase 3 efficacy multicentre trial in United States (US) showed 94.1% efficacy of the Spikevax at preventing COVID-19 illness, including severe disease. Aside from transient local and systemic reactions, no safety concerns were identified. Pregnant women were not eligible to participate in that trial.² Preliminary findings from an observational study in the US were not indicative of obvious safety signals among pregnant persons who received mRNA COVID-19 vaccines, but the study indicated the need for longitudinal follow-up in a large number of women.³

Spikevax was authorised across the European Union (EU), following conditional marketing authorisation by the European Commission on 6 January 2021⁴ and was approved on 08 January 2021 by the United Kingdom (UK) Medicines and Healthcare products Regulatory Agency (MHRA).⁵ Currently, Spikevax is indicated for active immunisation to prevent COVID-19 caused by SARS-CoV-2 in individuals 18 years of age and older.¹ According to the 28 May update the UK Joint Committee on Vaccination and Immunisation recommends that is that COVID-19 vaccines should be offered to pregnant women at the same time as the rest of the population, in line with the age group roll out.⁶ At the same time, a multinational cohort study showed that COVID-19 infection in pregnancy was associated with increased in severe maternal morbidity and mortality and with neonatal complications.⁷ Thus, an uptake of COVID-19 vaccination among pregnant women should be expected. Indeed, as of 21 July 2021 the Danish Health Authority recommended vaccination of pregnant women in second or third trimester, citing similar recommendations in 20 countries. Vaccination of some or all pregnant women is recommended in Denmark⁸ and Spain, permitted in the UK, and permitted with qualifications in Italy, according to Covid-19 Maternal Immunization Tracker, provided by Johns Hopkins University.⁹

Use of COVID-19 Moderna Vaccine in pregnancy and its effect on the mother and the neonate are currently not fully understood.¹⁰ This postauthorisation safety study (PASS), aims to describe use of Spikevax use in pregnancy and to examine any potential association between Spikevax vaccination and pregnancy complications, and adverse pregnancy and neonatal outcomes. This study is a Category 3 Required Pharmacovigilance Activity in the RMP. Safety of the Spikevax in the general population is examined in a separate, dedicated PASS (reference number mRNA-1273-P904)

8. Research question and objectives

The overarching research question is: is there a greater risk or prevalence of pregnancy complications, adverse pregnancy outcomes, or adverse neonatal outcomes following pregnancies exposed to Spikevax compared with pregnancies unexposed to Spikevax?

8.1. Primary objectives

- To determine whether exposure to the Spikevax during pregnancy is associated with an increased risk of:
 - a. Pregnancy complications
 - b. Adverse pregnancy outcomes
 - c. Major congenital malformations in the offspring (overall and organ-specific if feasible)
 - d. Adverse neonatal outcomes

8.2. Secondary objectives

- To describe utilization of Spikevax in pregnancy, overall and by trimester of pregnancy

Depending on the outcome, either a prevalence design (all endpoints except pregnancy-related death and neonatal death) or cohort design (pregnancy-related death and neonatal death) will be used to address each objective.

9. Research methods

This protocol is prepared based on the methodology developed as part of the European Medicines Agency's infrastructure to support the monitoring of the efficacy and safety of COVID-19 treatments and vaccines when used in day-to-day clinical practice, specifically the CONSIGN project (COVID-19 infectiOn aNd medicineS In preGNancy). This project is ongoing and all Data Access Providers (DAPs) participating in this study also contribute to CONSIGN. The CONSIGN project is collecting data on the impact of COVID-19 in pregnancy in order to guide decision-making about vaccine indications, vaccination policies and treatment options for COVID-19 in pregnant women. CONSIGN will analyse existing data sources (e.g. electronic health records, hospital data) and cohorts of pregnant women to provide information on the effect of infection and its treatments in different trimesters of pregnancy and on neonates.¹¹

9.1. Study design

9.1.1 Prevalence study

The pregnancy complications, adverse pregnancy outcomes (except pregnancy-related death), and neonatal outcomes (except neonatal death) will be addressed using the prevalence study

design. In the routinely collected data, pregnancies are identifiable on the date of pregnancy end, either in a birth or in an abortive outcome. All identifiable pregnancies will be included, and their start and end dates will be estimated based on the first day of the last menstrual period (LMP) or gestational age at end, depending on data availability. Outcomes examined in this design include gestational diabetes, hypertensive disorders of pregnancy, fetal growth restriction/small for gestational age, abortive outcomes, stillbirth, preterm birth, major congenital malformations, microcephaly (head circumference), and ectopic pregnancy..

Risk of adverse and pregnancy outcomes will be compared in births exposed and unexposed to Spikevax. The measure of association will be prevalence ratio.

9.1.2 Cohort study

For the outcomes neonatal death, and pregnancy-related death, and postpartum bleeding, a cohort design will be employed.

Risk of neonatal (28-days postnatally) death will be compared in liveborn neonates exposed and unexposed to Spikevax in utero or during the periconceptional period. The measure of association will be the risk ratio.

Pregnancy-related deaths will be assessed by comparing deaths among pregnant women exposed and unexposed to Spikevax between 30 days before LMP and delivery date. A given pregnancy will be considered exposed from the recorded date of the first Spikevax dose receipt. The measure of association will be mortality rate ratio.

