9.2.3 Study Period

In the prevalence study, there is no follow-up per se, as study population will be assembled based on existing (prevalent) outcomes.

In the cohort study, for the outcome of neonatal death, the maximum follow-up will be 28 days postnatally, censored at emigration or end of data. For the outcome pregnancy-related death, the maximum follow-up will be 1 year after pregnancy end,¹² censored by emigration or end of data availability.

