9.3.2 Outcome

9.3.2.1 Primary outcomes

The following outcomes will be assessed, noting that outcome-specific analytic considerations such as the etiologically relevant exposure window and specific additional population restrictions (e.g., exclusion of women with teratogenic medication exposure or teratogenic infections for assessment of major congenital malformations) will be defined in the SAP.

- Pregnancy complications are:
 - Hypertensive disorders of pregnancy (preeclampsia, eclampsia, gestational hypertension)
 - Gestational diabetes
 - Bleeding during pregnancy
 - Postpartum haemorrhage
 - Pregnancy-related death

- Adverse pregnancy outcomes are:
 - Fetal death (spontaneous abortion or stillbirth)
 - Termination of pregnancy for fetal anomaly (TOPFA)
 - Any elective pregnancy termination
 - Ectopic pregnancy

- Adverse neonatal outcomes are:
 - Fetal growth restriction/small for gestational age (SGA), using sex- and gestational-age specific cutoffs¹³
 - Preterm birth (<37 full gestational weeks)
 - Low birth weight (<2500 g)
 - Major congenital malformations¹⁴
 - Microcephaly (based on head circumference)
 - Low 5-minute Apgar score
 - Neonatal death (death within 28 days of birth)

Where a signal is detected for the outcome of major congenital malformation as a composite, organ system-specific analyses will be conducted. Organ-specific major congenital malformations, according to the EUROCAT¹⁴ classification are:

- Nervous system
- Eye
- Ear, face and neck
- Congenital heart defects
- Respiratory

- Oro-facial clefts
- Digestive system
- Abdominal wall defects
- Urinary
- Genital
- Limb
- Other

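### Postpartum haemorrhage is assigned to two designs, has no measure or follow-up end under the cohort one, and is counted in Table 4 over pregnancies that cannot have the event

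*Protocol*

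**What the plan says.** **Prevalence design.** Protocol 8.2, repeated in the abstract, says that "either a prevalence design (all endpoints except pregnancy-related death and neonatal death) or cohort design (pregnancy-related death and neonatal death) will be used". Only the two deaths are excepted. Section 9.1.1 agrees: "The pregnancy complications, adverse pregnancy outcomes (except pregnancy-related death), and neonatal outcomes (except neonatal death) will be addressed using the prevalence study" design, compared in births by a prevalence ratio. Section 9.3.2.1 lists "Postpartum haemorrhage" among the pregnancy complications, so it falls under that sentence.

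**Cohort design.** Section 9.1.2 says: "For the outcomes neonatal death, and pregnancy-related death, and postpartum bleeding, a cohort design will be employed". Bleeding during pregnancy is a separate entry in 9.3.2.1, so postpartum bleeding can only be this outcome.

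**What the cohort section then specifies.** Neonatal death gets a risk ratio. Pregnancy-related death gets a mortality rate ratio, comparing women "exposed and unexposed to Spikevax between 30 days before LMP and delivery date", with the rule "A given pregnancy will be considered exposed from the recorded date of the first Spikevax dose receipt". Neither is assigned to haemorrhage. Section 9.2.3 gives an end of follow-up for the two deaths only: "for the outcome of neonatal death, the maximum follow-up will be 28 days postnatally", and one year after pregnancy end for pregnancy-related death.

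**Table 4 and 9.7.3.** Table 4 gives postpartum haemorrhage the population of all pregnancies and exposure at any time in pregnancy, with no outcome window. Section 9.7.3 assigns log-binomial regression to prevalences and risks and Cox regression to rate ratios. It names no time scale and does not say which model applies here.

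**The concern.** Design is something this protocol fixes itself rather than leaving to the SAP, and for this outcome it fixes it in two incompatible ways. An SAP that follows one section breaks the other. All five databases are to run one common program (9.6), so that program needs a single instruction.

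Two features make the choice more than a matter of labels. First, haemorrhage can occur only at or after delivery, so pregnancy time is event-free by definition. A rate that puts pregnancy time in the denominator, and counts exposed time only from the dose, gives vaccinated and unvaccinated women different amounts of that empty time. Second, the all-pregnancies population includes spontaneous and induced abortions and ectopic pregnancies. These cannot have the event, and because they are short they leave less time to be vaccinated. They therefore collect in the unexposed denominator and dilute its prevalence.

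**Working it through.** The protocol states no figure for this outcome, so there is none to reproduce. The check asks what each readable analysis would return when the vaccine has no effect.

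**Inputs from the protocol**
- Unexposed-to-exposed ratio k = 5, 10 or 20, and true ratio 1 (Table 3).
- Spontaneous abortion prevalence 20% (an example value in Table 3).
- Maternal cohort window starting 30 days before LMP, exposure from first dose (9.1.2, written for pregnancy-related death).
- Trimester limits (9.3.1), which give mid-trimester days of about 49, 150 and 241 if delivery is at day 280.

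**Assumptions not in the protocol**
- Delivery at about day 280.
- Haemorrhage risk 5%, unrelated to gestational length. The risk cancels in the closed-form ratios.
- First-dose day as stated in each step.
- Early losses at days 42 to 98.

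**1. Ratio among deliveries.** If risk p is the same in both groups and exposure is classified at delivery, the ratio is p/p = 1. A simulation (8 runs of 60,000 births, delivery centred on day 280, one in six vaccinated, dose day uniform over 0 to 280) gave a mean of 0.99, with runs from 0.91 to 1.04. One run has about 500 exposed and 2,500 unexposed events, so a standard error of about √(0.95/500 + 0.95/2,500) = 0.05 on the log scale. That spread is chance.

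**2. Table 4's denominator.** Let u be the proportion vaccinated among deliveries, and let 20% of pregnancies be lost at day e, with a chance u·e/280 of having been vaccinated by then. The null prevalence ratio is the share of deliveries among the exposed divided by the share among the unexposed.
- u = 1/6, e = 42. Exposed: 0.1333/(0.1333 + 0.0050) = 0.964. Unexposed: 0.6667/(0.6667 + 0.1950) = 0.774. Ratio 1.25.
- u = 1/21, e = 98. Exposed: 0.0381/(0.0381 + 0.0033) = 0.920. Unexposed: 0.7619/(0.7619 + 0.1967) = 0.795. Ratio 1.16.

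All combinations of u = 1/6, 1/11, 1/21 and e = 42, 70, 98 lie between 1.16 and 1.25.

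**3. Crude person-time rate, if the rule for pregnancy-related death were borrowed.** With first dose on day v and f days of follow-up after delivery, the null rate ratio is [1/(280 − v + f)] ÷ [k/(k(310 + f) + v + 30)]. An event on the delivery day is counted, and time is not stopped at the event. For v = 140, f = 0, k = 5: (1/140) ÷ (5/1,720) = 2.46. Ranges over k = 20 to 5:

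| Follow-up ends | Dose day 49 | Day 140 | Day 150 | Day 241 |
|---|---|---|---|---|
| Delivery (9.1.2 window) | 1.36–1.41 | 2.27–2.46 | 2.45–2.66 | 8.3–9.3 |
| 42 days after (assumed) | 1.30–1.35 | 1.98–2.12 | 2.10–2.26 | 4.5–5.0 |
| 365 days after (9.2.3) | 1.14–1.16 | 1.35–1.40 | 1.38–1.44 | 1.70–1.80 |

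The simulated data of step 1, analysed this way to delivery, gave 2.37.

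**4. Cox regression with time-varying exposure on gestational age.** The same simulated data gave 0.99. Women are compared at the same gestational age, so the event-free time does no harm.

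**The case against.** The best reply is that this is a wording slip. Section 9.1.2 names the outcome explicitly, the outcome list in 9.1.1 omits it, and an event ascertained after pregnancy end fits a cohort risk. The abstract also assigns outcomes to designs in two ways, since one sentence there moves neonatal outcomes generally to the cohort design. In the same population with the same fixed exposure, a log-binomial risk ratio and a prevalence ratio are the same number, so the label alone need not alter anything. An ascertainment window and a Cox time scale are also ordinary SAP content, and 9.3.2.1 does leave outcome-specific considerations to the SAP.

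Much of this stands. The cohort design may be the intended one, and the unnamed time scale is no fault in itself. What does not fall away is that 8.2 and 9.1.1 exclude what 9.1.2 requires, that 9.1.2 leaves its own assignment unfinished, and that Table 4 fixes an unsuitable denominator under either design.

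A reader might go further and infer that the cohort analysis would double the ratio and make the vaccine look harmful by construction. The protocol does not support that. The first-dose rule, the window and the mortality rate ratio stand in the paragraph on pregnancy-related death and are not extended to haemorrhage. The other rule in the same section, a risk ratio for neonatal death, would give about 1. A value near 2 needs an assumed mid-pregnancy dose, follow-up stopping at or soon after delivery, and a crude rate. With the one-year follow-up of 9.2.3, a day-140 dose gives 1.35 to 1.40. Taken literally, a window that ends at delivery would also exclude or truncate a postpartum event.

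**Conclusion.** The point holds as a contradiction and an unfinished specification for a primary outcome. It needs no number to stand.

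On size, under no effect:
- A prevalence or risk ratio among deliveries is about 1, given haemorrhage risk unrelated to gestational length.
- Table 4's all-pregnancies denominator gives roughly 1.2 (1.16 to 1.25), given 20% loss at days 42 to 98 and uniform dose timing. Of the distortions shown, this is the only one that follows from a rule the protocol actually writes for this outcome. The loss timing and dose timing are assumed.
- A crude rate from first dose gives about 1.1 to 9. This is conditional on borrowing a rule written for another outcome, and the width of the range reflects inputs that the protocol does not give.
- Cox regression on gestational age gives about 1.

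It should be corrected before the common program is written. It does not show that the study would report a false signal.

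**What to change.** Assign postpartum haemorrhage to one design and say so consistently in the abstract, 8.2, 9.1.1, 9.1.2 and 9.2.3. The shortest route is to remove it from the opening sentence of 9.1.2 and add it to the outcome list in 9.1.1. If the sponsor prefers the cohort label, the exceptions in 8.2, the abstract and 9.1.1 must be amended and a risk ratio named in 9.1.2.

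Under either label:
- Change its Table 4 population to pregnancies ending in live birth or stillbirth.
- Classify exposure as of delivery.
- Estimate a prevalence ratio (equivalently a risk ratio) by log-binomial regression.
- State one fixed postpartum ascertainment window for all databases in 9.2.3 or the SAP.
- State that the first-dose person-time rate rule for pregnancy-related death does not apply to it.

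The cost is a few sentences and one row of Table 4. No new data are needed: the restriction uses the type of pregnancy end, which the inclusion criteria already rely on.
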